12.3 Baseline Visit

Baseline values will be recorded from 1 to 7 days prior to the treatment visit. The following procedures will be performed during the Baseline Period:

- Physical exam
- Assessment of Adverse Events and Concomitant Medications
- Documentation of bleeding episodes and FVIII usage (by either subject or clinical information)
- Distribution of subject diaries and training in diary completion
- Blood chemistry, haematology, urine tests, coagulation screen, and CRP (refer to Table 9.7.8.2.1)
- PBMC collection for CTL baseline
- PCR of vector genomes in blood, saliva, urine, semen, and stools
- Exploratory biomarker assessments
- Haemo-QoL-A QoL assessment

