9.3.3.1 Study Safety Evaluation Criteria

If any of the following events occur in a subject in the study who has received BMN 270 infusion, enrollment into the trial will be put on halt to complete an extensive safety analysis per Section 9.1.

- A 5-fold increase from baseline in ALT after BMN 270 administration
- The occurrence of Grade 3 or higher adverse events assessed as related to study drug, including liver failure and clinical hepatitis
- Grade 2 adverse event assessed as related to study drug that persists for at least 7 days
- The detection of neutralizing antibodies to hFVIII following BMN 270 infusion
- The persistent detection of the AAV vector genome in the semen of a participant more than 26 weeks after BMN 270 infusion, as discussed in Section 9.7.8.5
- The occurrence of a malignancy excluding skin cancers at any point after BMN 270 infusion

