12.2 Screening Visit

Screening assessments will be performed within 28 days (\pm 14 days) of BMN 270 infusion while baseline assessments will take place within 7 days of BMN 270 infusion (Day 1). Should the screening visit occur within 7 days of the drug infusion, physical examination, vital signs, blood chemistry, haematology, urine tests, coagulation screen, and CRP do not need to be repeated at Baseline.

The following procedures will be performed during the Screening Period:

- Full medical history, including haemophilia A history, Hepatitis B, Hepatitis C, and HIV.
- Complete Physical Exam (including height and weight)
- Vital Signs (systolic and diastolic blood pressure, heart rate, respiration rate, and temperature)
- Assessment of Adverse Events and Concomitant Medications
- Documentation of bleeding episodes and FVIII usage (by either subject or clinical information)
- Electrocardiogram
- Chest X-ray
- Liver Ultrasound
- Samples for hFVIII Assays
 - Baseline hFVIII activity chromogenic FXa (plasma)
 - o Baseline hFVIII activity level one-stage APTT assay
 - o hFVIII coagulation activity exploratory assay
 - o hFVIII inhibitor level (Bethesda assay with Nijmegen modification)
 - hFVIII total antibody assay
 - hFVIII antigen (ELISA)

- Blood sample for AAV5 Assays
 - o AAV5 antibody titer
 - AAV5 transduction inhibition assay
- Screen for Hepatitis B, Hepatitis C, and HIV if required (subjects with documented negative results 30 days prior to informed consent being obtained do not need to be retested)
- Blood chemistry, haematology, urine tests, coagulation screen, and CRP (refer to Table 9.7.8.2.1)
- Blood samples for Biomarker testing (including HLA genotyping, FVIII genotyping status, TNFα and IL10a single nucleotide polymorphisms)

12.2.1 "Smart Rescreening" Visit

Subjects who undergo smart rescreening must complete the rescreening assessments and receive the infusion within 90 days of signing the original consent. Subjects who do not complete dosing within 90 days will be required to re-consent and undergo all screening procedures. Subjects may not undergo smart rescreening more than once.

If a patient has to be screened again because the original assessments have fallen out of the 28 + 14 day period allowed for Screening (refer to Section 12.2), then only the following assessments need to be performed (rather than the full list indicated in Section 12.2) for the patient to be successfully re-screened for the study:

- Vital signs

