- Assessment of Adverse Events and Concomitant Medications
- Documentation of bleeding episodes and FVIII usage (by either subject or clinical information)
- hFVIII Assays (only the hFVIII inhibitor level (Bethesda assay with Nijmegen modification)
- Blood sample for AAV5 Assays
 - AAV5 antibody titer
 - AAV5 transduction inhibition assay
- Blood chemistry, haematology, urine tests, coagulation screen, and CRP (refer to Table 9.7.8.2.1)

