12.4 Treatment Visit/BMN 270 Infusion Visit (Day 1)

There will be one treatment visit for each subject. Subjects will remain in the clinic for 24 hours for the BMN 270 Infusion Visit. The following procedures will be performed during the BMN 270 Infusion Visit:

- Physical exam
- Assessment of Adverse Events and Concomitant Medications
- Blood sample for AAV5 Assays (must be performed before the BMN 270 infusion)
 - o AAV5 antibody titer
 - o AAV5 transduction inhibition assay
- BMN 270 Infusion
- Vital Signs
 - Vital signs will be recorded prior to BMN 270 infusion and then every 15 minutes (± 5 minutes) during BMN 270 infusion. Following infusion, vital signs will be monitored every 1 hour (± 5 minutes) for the first 6 hours, every 2 hours (± 15 minutes) for the next 6 hours, and then at 4 hour (± 15 minutes) intervals for the remainder of the subject's stay in the clinic.

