14.6 Determination of Sample Size

No formal sample size calculations based on statistical power were performed.

The sample size is determined based upon clinical consideration and could detect a strong clinical efficacy signal. Up to 12 subjects may be dosed in the study; the actual number of subjects will depend on the criteria for dose escalation.

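### In the Amendment 3 text the last listed pre-infusion anti-FVIII inhibitor and total antibody samples are at Screening, up to 42 days before infusion (total antibody up to about 90 days after smart rescreening)

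*Protocol*

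**What the plan says.** All references are to Amendment 3 unless stated; it is the latest version in the part of the protocol at hand.

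- **Screening (12.2)** lists both tests: "hFVIII inhibitor level (Bethesda assay with Nijmegen modification" and "hFVIII total antibody assay". Section 12.2.1 describes the window as the "28 + 14 day period allowed for Screening".
- **Smart rescreening (12.2.1)** requires infusion within 90 days of the original consent. Its FVIII line is limited to one test: "hFVIII Assays (only the hFVIII inhibitor level (Bethesda assay with Nijmegen modification".
- **Baseline (12.3)**: "Baseline values will be recorded from 1 to 7 days prior to the treatment visit". The list includes blood cells for the T-cell baseline but no FVIII assay of any kind.
- **Day 1 (12.4)** has one pre-dose immunology line: "Blood sample for AAV5 Assays (must be performed before the BMN 270 infusion".
- **After infusion (12.5.1, 12.5.2)** the Bethesda assay is done on Day 4 and weekly to Week 16. The FVIII antibody titre is done weekly from Week 1.
- **Concentrate use (9.4.8.1)**: prophylaxis stops only on the day of infusion, and on-demand use is unrestricted before and after it.
- **Use of the data**: 9.7.4 compares rises in total antibody with FVIII activity, and 14.3 plans comparisons within participants. Section 9.3.3.1 lists as a reason to halt enrolment: "The detection of neutralizing antibodies to hFVIII following BMN 270 infusion".

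**The concern.** A rise in antibody, or a within-participant comparison, needs a reference value. The protocol names none for anti-FVIII antibody, so in practice it will be the last sample before infusion. For the other immune measures that sample is recent: AAV5 antibody on Day 1, and T cells within the preceding week. For anti-FVIII antibody it can be weeks or months old, although subjects remain exposed to the same protein through their concentrate for the whole interval.

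An antibody that appears or rises between Screening and infusion would first be seen in a post-infusion sample and could be read as a response to BMN 270. Describing the immune response to the FVIII transgene product is a secondary objective (Section 8, read here in the Amendment 2 text). With at most 12 subjects, a single misread case would be visible in the summary. No SAP can restore a pre-infusion sample that was never scheduled.

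**Working it through.** The plan states no figure for the age of the reference sample, and no power calculation is involved (14.6: "No formal sample size calculations based on statistical power were performed"). The check therefore compares the procedure lists and counts days.

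| Visit (Amendment 3) | Timing | Bethesda inhibitor | Anti-FVIII total antibody |
|---|---|---|---|
| Screening, 12.2 | up to 42 days before infusion | yes | yes |
| Smart rescreening, 12.2.1 | infusion within 90 days of consent | yes | no |
| Baseline, 12.3 | 1 to 7 days before | no | no |
| Day 1 pre-dose, 12.4 | 0 days | no | no |
| Day 4, 12.5.2 | after infusion | yes | no |
| Weeks 1 to 16, 12.5.1 | after infusion | yes | yes |

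**Maximum age of the last listed pre-infusion sample**

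- Without rescreening, both tests: 28 + 14 = 42 days, which is 42 / 7 = 6 times the Baseline window.
- With rescreening, total antibody: more than 42 and up to 90 days, or 90 / 7 = 12.9 times the Baseline window. The upper end needs a Screening sample drawn on the day of consent and infusion on the last permitted day.
- With rescreening, inhibitor: if it is redrawn on the first day outside the 42-day window (day 43), has no window of its own, and infusion is on day 90, then 90 − 43 = 47 days.

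**Concentrate exposures inside the gap.** Assume 2 to 3 prophylactic infusions a week. This figure comes from the background text of the Amendment 2 synopsis; it is not a trial requirement and does not describe on-demand subjects.

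- 42 days: 6 weeks × 2 to 3 = 12 to 18.
- 90 days: 12.86 weeks × 2 to 3 = 25.7 to 38.6, about 26 to 39.
- 7 days: 2 to 3. Day 1 pre-dose: none.

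These are counts of exposures, not an incidence of new antibody. The documents give no incidence.

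**Weight of one misread case.** 1/4 = 25% of a cohort of four (9.4.6.2 allows up to four); 1/12 = 8.3% of the maximum enrolment in 14.6.

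**Effect of the change.** A pre-dose Day 1 sample takes the maximum age from 42 days (total antibody up to 90) to 0. The cost is 2 assays × at most 12 subjects = 24.

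**The case against.** The best counter-argument is that early post-infusion samples do much of the work. Expression is expected to be near its maximum at about three weeks (Amendment 2, 9.1, repeated in the Amendment 3 change log). A positive Bethesda on Day 4 or at Week 1 would therefore point to an antibody already present. Blood is also drawn at Baseline and on Day 1 for other purposes, and 9.7.6 allows exploratory reuse of samples. A reader might infer that a case arising in the gap could never be re-attributed; these provisions mean the documents do not support that. The mitigation is still partial. Day 4 has no antibody titre, no post-infusion sample is designated as a reference, and no aliquot is reserved for this test.

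Second, the omission looks deliberate. Amendment 2 listed both tests at Baseline, and the Amendment 3 change log includes the FVIII assays among its changes to 12.3. That stands, and a Screening reference does exist; the point is its age.

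Third, a Day 1 sample cannot tell a concentrate-induced antibody from a transgene-induced one arising later, because concentrate may be used after infusion. That also stands. The fix closes the gap before infusion only.

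Fourth, entry requires at least 150 exposure days and limits on inhibitor history. New antibody in the gap is therefore probably rare, though these criteria supply no reference titre.

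**Conclusion.** The point holds as an inexpensive improvement to the sampling schedule. The reference for anti-FVIII inhibitor and total antibody can be 42 days old, and for total antibody in smart-rescreened subjects up to about 90. The likely number of misread cases is small and cannot be estimated from the documents.

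Three stronger readings should be resisted.

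- A reader might attach the 90-day gap to the enrolment halt. The halt depends on neutralizing antibody, which smart rescreening repeats, so the relevant gap there is 42 days, or 47 at most on the assumption stated above.
- A reader might conclude that the halt criterion should be judged against a Day 1 value. As written it depends on detection after infusion, without attribution, and leads to a safety review with possible restart (9.1, Amendment 2 text). Nothing here justifies narrowing it.
- A reader might conclude that no Baseline sample exists at all. The Amendment 3 version of Table 9.1.1 is not in the part shown. The Amendment 2 table marked hFVIII assays at Baseline, and the visible change-log entries for that table do not mention removing the mark. If it remains, the table and 12.3 disagree.

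The conclusion assumes that the Section 12 lists govern, and that the last pre-infusion sample serves as the reference, which the protocol does not state.

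**What to change.** In 12.4, add a Bethesda assay and an anti-FVIII total antibody titre to the blood already drawn before infusion for AAV5. Name that result as the reference for the immunogenicity analysis under 9.7.4 and 14.3, and make it available as attribution information in any safety review. The infusion need not wait for the result. Leave the halt criterion in 9.3.3.1 unchanged.

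Check Table 9.1.1 of Amendment 3 and reconcile it with 12.3 if they differ.

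The cost is at most 24 assays and a line in the schedule, with no extra visit. The change helps only subjects not yet dosed.

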12.4 Treatment Visit/BMN 270 Infusion Visit (Day 1)

There will be one treatment visit for each subject. Subjects will remain in the clinic for 24 hours for the BMN 270 Infusion Visit. The following procedures will be performed during the BMN 270 Infusion Visit:

- Physical exam
- Assessment of Adverse Events and Concomitant Medications
- Blood sample for AAV5 Assays (must be performed before the BMN 270 infusion)
 - o AAV5 antibody titer
 - o AAV5 transduction inhibition assay
- BMN 270 Infusion
- Vital Signs
 - Vital signs will be recorded prior to BMN 270 infusion and then every 15 minutes (± 5 minutes) during BMN 270 infusion. Following infusion, vital signs will be monitored every 1 hour (± 5 minutes) for the first 6 hours, every 2 hours (± 15 minutes) for the next 6 hours, and then at 4 hour (± 15 minutes) intervals for the remainder of the subject's stay in the clinic.

12.5 BMN 270 Infusion Follow-Up Visits

After BMN 270 has been infused, subjects will return to the study site every week $(\pm 48 \text{ hours})$ for 16 weeks, when the following procedures will be completed:

12.5.1 Every Visit

Every week (Weeks 1 through 16), the following procedures will be performed:

- Physical exam
- Assessment of Adverse Events and Concomitant Medications (including review of subject diary for bleeding and FVIII use)
- Vital Signs
- Blood chemistry, haematology, urine tests, coagulation screen, and CRP (refer to Table 9.7.8.2.1)
 - Each subject will have comprehensive surveillance plan monitoring LFTs once a week from dose to completion of Week 6, 3 times per week (every other day excluding weekends) from Weeks 7 to 12, and once a week from Weeks 13 to 16. If a subject's ALT is found to be greater than 1.5x baseline during these periods, then LFTs will be monitored three times per week or until the ALT returns to baseline.
- Samples for FVIII Assays
 - FVIII activity level (APTT)
 - FVIII activity level (chromogenic FXa assay)
 - FVIII coagulation activity exploratory assay
 - o Bethesda assay (with Nijmegen modification) for hFVIII inhibitor level
 - FVIII antigen (ELISA)

Note: If a subject has used FVIII within 72 hours of a measurement day, all efforts should be made to obtain FVIII activity measurements when a 72-hour interval without FVIII use is achieved.

- FVIII antibody titer
- PCR of vector genomes in blood, saliva, urine, semen, and stools
 - Collection to occur weekly until at least 3 consecutive negative results are obtained

12.5.2 Week 1 – Day 2 and Day 4

On Day 2 and Day 4 of Week 1, the following procedures will be performed:

- PCR of vector genomes in blood, saliva, urine, semen, and stools (Day 2 and Day 4)
- Samples for FVIII Assays (Day 4 only)
 - FVIII activity level (APTT)
 - FVIII activity level (chromogenic FXa assay)
 - FVIII coagulation activity exploratory assay
 - o Bethesda assay (with Nijmegen modification) for hFVIII inhibitor level
 - FVIII antigen (ELISA)

Note: If a subject has used FVIII within 72 hours of a measurement day, all efforts should be made to obtain FVIII activity measurements when a 72-hour interval without FVIII use is achieved.

12.5.3 Every 2 Weeks

Every 2 weeks (Weeks 2, 4, 6, 8, 10, 12, 14 and 16), the following procedure will be performed:

• Exploratory biomarker assessments

12.5.4 Weeks 4, 8, 12, and 16

At Weeks 4, 8, 12, and 16, the following procedure will be performed:

• PBMC collection

12.5.5 Weeks 1, 3, and 6

At Weeks 1, 3, and 6, the following procedure will be performed:

• Test for Hepatitis B and Hepatitis C reactivation

12.5.6 Weeks 8 and 16

At Weeks 8 and 16, the following procedure will be performed:

• AAV5 antibody titer

12.5.7 Weeks 1, 2, 3, 4, and 16

At Weeks 1, 2, 3, 4, and 16, the following procedure will be performed:

• Haemo-QoL-A QoL assessment

12.6 Safety Follow-Up – Year 1

After the 16 weekly infusion follow-up visits are complete, subjects will return to the study site at Weeks 20, 28, 36, 44, and 52 (\pm 1 week), when the following procedures will be completed:

12.6.1 Every Visit

At Weeks 20, 28, 36, 44, and 52, the following procedures will be performed:

- Physical exam
- Assessment of Adverse Events and Concomitant Medications (including review of subject diary for bleeding and FVIII use)
- Vital Signs
- Blood chemistry, haematology, urine tests, coagulation screen, and CRP (refer to Table 9.7.8.2.1)
- FVIII Assays
 - FVIII activity level (APTT)
 - FVIII activity level (chromogenic FXa assay)
 - FVIII coagulation activity exploratory assay
 - o Bethesda assay (with Nijmegen modification) for FVIII inhibitor level
 - FVIII antigen (ELISA)

Note: If a subject has used FVIII within 72 hours of a measurement day, all efforts should be made to obtain FVIII activity measurements when a 72-hour interval without FVIII use is achieved.

- AAV5 antibody titer
- FVIII antibody titer
- PBMC collection
- PCR of vector genomes in blood, saliva, urine, semen, and stools
 - Sample testing during Safety Follow-Up is not required if at least 3 consecutive samples are clear during the Post-Infusion Follow-Up period.

12.6.2 Weeks 28 and 52

At Weeks 28 and 52, the following procedure will be performed:

• Haemo-QoL-A QoL assessment

12.7 Safety Follow-Up – Years 2-5

During Years 2-5 of Safety Follow-up, subjects will be assessed every 3 months (\pm 2 weeks). At these times, the following procedures will be completed:

12.7.1 Every Visit

Every 3 months (\pm 2 weeks), the following procedures will be performed:

- Physical exam
 - Complete Physical Exam will be performed every 52 weeks; Brief Physical Exams may be performed at other visits.
- Assessment of Adverse Events and Concomitant Medications (including review of subject diary for bleeding and FVIII use)
- Blood chemistry, haematology, urine tests, coagulation screen, and CRP (refer to Table 9.7.8.2.1)
- FVIII Assays
 - FVIII activity level (APTT)
 - FVIII activity level (FXa chromogenic assay)
 - FVIII coagulation activity exploratory assay
 - o Bethesda assay (with Nijmegen modification) for FVIII inhibitor level
 - o FVIII antigen (ELISA)

Note: If a subject has used FVIII within 72 hours of a measurement day, all efforts should be made to obtain FVIII activity measurements when a 72-hour interval without FVIII use is achieved.

- AAV5 antibody titer
- FVIII antibody titer
- PBMC collection
- PCR of vector genomes in blood, saliva, urine, semen, and stools
 - Sample testing during Safety Follow-Up is not required if at least 3 consecutive samples are clear during the Post-Infusion Follow-Up period.
- Vital Signs

12.7.2 Every Other Visit (Every 6 Months)

Every six months starting at the Week 78 visit (ie, 26 weeks after the Week 52 visit at the end of Year 1 of the Safety Follow-up period), the following procedure will be performed:

• Haemo-QoL-A QOL assessment

12.8 Early Termination Visit

The Early Termination visit will occur on the date the subject withdraws from the study, even if the date does not correspond to a protocol-specific visit.

If a subject leaves the study prior to the Week 260 visit, the subject will be asked to return to the study site and complete an Early Termination visit. At the Early Termination visit, as many of the following assessments as possible should be done:

- Physical exam
- Assessment of Adverse Events and Concomitant Medications (including review of subject diary for bleeding and FVIII use)
- Blood chemistry, haematology, urine tests, coagulation screen, and CRP (refer to Table 9.7.8.2.1)
- FVIII Assays
 - FVIII activity level (APTT)
 - FVIII activity level (chromogenic FXa assay)
 - o FVIII coagulation activity exploratory assay
 - o Bethesda assay (with Nijmegen modification) for FVIII inhibitor level
 - FVIII antigen (ELISA)

Note: If a subject has used FVIII within 72 hours of a measurement day, all efforts should be made to obtain FVIII activity measurements when a 72-hour interval without FVIII use is achieved.

- AAV5 antibody titer
- FVIII antibody titer
- PBMC collection
- PCR of vector genomes in blood, saliva, urine, semen, and stools
 - Sample testing at the ETV is not required if at least 3 consecutive samples are clear during the Post-Infusion Follow-Up period.
- Vital Signs

BOMARIN[®]

• Haemo-QoL-A QOL assessment

12.9 End of Study

The study will end after the last subject completes the last Safety Follow-Up visit (Week 260). BioMarin reserves the right to discontinue the study any time for clinical or administrative reasons and to discontinue participation of an individual investigator or site for clinical or administrative reasons, including, but not limited to, poor enrollment or noncompliance with procedures of the protocol or GCP. In addition, the study may be terminated if, in the opinion of BioMarin, the safety of the study subjects may be compromised.

13 DATA QUALITY ASSURANCE

BioMarin personnel or designees will visit the study site prior to initiation of the study to review with the site personnel information about the IP, protocol and other regulatory document requirements, any applicable randomization procedures, source document requirements, eCRFs, monitoring requirements, and procedures for reporting AEs, including SAEs.

At visits during and after the study, a CRA will monitor the site for compliance with regulatory documentation, with a focus on accurate and complete recording of data on eCRFs from source documents, adherence to protocol, randomization (if applicable), SAE reporting and drug accountability records.

Data quality control and analysis will be performed by BioMarin or a designee, based on a predefined analysis plan.

14 STATISTICAL METHODS AND DETERMINATION OF SAMPLE SIZE

14.1 Statistical and Analytical Plans

The statistical analysis plan (SAP) will provide additional details on the planned statistical analysis. Unless otherwise stated, all analyses will be performed using SAS.

14.1.1 Interim Analyses

No formal interim analysis is planned. An analysis of the primary endpoint will be done following all subjects having completed the study assessments through the end of the Post-Infusion Follow-Up Period (Week 16).

